7.4.3 Coding

Coding of AEs will be performed on an ongoing basis throughout the study by Accelovance Safety. Verbatim terms that are entered into the database by the site will be coded manually; if necessary a query will be created to obtain clarification from the site. These events will be mapped to the MedDRA (Version 20.0) system for reporting (preferred term [PT] and system organ class [SOC]). Medical/surgical history will also be coded using MedDRA (Version 20.0).

Concomitant medications will be coded using World Health Organization (WHO) Drug Global Dictionary (March 1, 2017).

7.4.4 Statistical Software

Data manipulation, tabulation of descriptive statistics, calculation of inferential statistics, and graphical representations will be performed primarily using SAS (release 9.2 or higher) for Windows. If the use of other software is warranted, the final clinical study report will detail what software was used and for what purposes.

7.4.5 Derived Variables

- Non Treatment Emergent Adverse Events include all AEs that stopped the day prior to the vaccination, or started prior to the vaccination but did not increase in severity or relationship during treatment.
- Treatment Emergent Adverse Events (TEAEs) include all AEs that start on or after vaccination, or AEs that are present prior to vaccination, but their severity or relationship increases after the vaccination date
- Change from baseline will be calculated as the observed value at the current visit or time point minus the observed value at baseline.
- Prior medications include all medications that have a start date prior to the date of vaccination.
- Concomitant medications include all medications that are taken on or after the date of vaccination.

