
 To describe the safety profile of NasoVAX in healthy adults when administered by intranasal spray at a single dose of 1×10^9, 1×10^{10}, or 1×10^{11} viral particles (vp) 	
 Reactogenicity: counts and percentages of subjects with local events (nasal irritation, sneezing, nasal congestion, cough, sore throat, change in smell, change in taste, change in vision, eye pain) and systemic events (headache, fatigue, muscle ache, nausea, vomiting, diarrhea, chills, fever) for 14 days after vaccination Adverse Events (AEs): counts and percentages of subjects with AEs from Day 1 to Day 29; medically attended adverse events (MAEs), serious adverse events (SAEs), new-onset chronic illness (NCI) from Day 1 to Day 181
Secondary Objective	

 To evaluate the humoral immune response to NasoVAX when administered by intranasal spray at a single dose of 1×10^9, 1×10^{10}, or 1×10^{11} vp 	
 Antibody level measured by hemagglutination inhibition (HAI) in serum: 
 Geometric mean titer (GMT): the antilog of the mean of the log-transformed titers Geometric mean ratio (GMR): the ratio of postvaccination and prevaccination GMTs within the same dose group Seroprotection rate (SPR): the percentage of subjects with a HAI titer $\geq 1:40$ Seroconversion rate (SCR): the percentage of subjects with either a baseline HAI titer $< 1:10$ and a postvaccination titer $\geq 1:40$ (which is 4 times the assay lower limit of quantitation), or a baseline HAI titer $\geq 1:10$ and a 4-fold increase in postvaccination HAI titer relative to baseline Antibody level measured by microneutralization (MN) in serum: 
 GMT Responder rate: the proportion of subjects with 2-fold and 4-fold rise since baseline

OBJECTIVES	ENDPOINTS
Exploratory Objectives	

 To evaluate the cellular immune response to NasoVAX when administered by intranasal spray at a single dose of 1×10^9, 1×10^{10}, or 1×10^{11} vp 	
 Spot-forming units (SFUs) to hemagglutinin (HA) peptides measured by enzyme-linked immunosorbent spot assay (ELISpot) in peripheral blood mononuclear cells (PBMCs): 
 Geometric mean SFUs Responder rate: the number and percentage of subjects with 3-fold rise since baseline and 25 SFU/million cells greater than baseline

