All AEs and medications will be recorded from signing of the informed consent form to Day 29. Thereafter to the end of the study, only MAEs, NCIs, SAEs, immunosuppressive medications (see list in Appendix 3), and vaccines will be recorded. Samples for clinical laboratory tests (hematology, serum chemistry, urinalysis) will be collected at Screening and on Days 8 and 29. A complete physical examination and vital signs will be performed at Screening and predose on Day 1, and targeted and symptom-driven physical examinations will be performed and vital signs measured 2 hours postdose and on Days 4, 8, 15, and 29. An electrocardiogram (ECG) will be performed at Screening and on Day 29. If a subject experiences acute symptoms compatible with adenoviral infection within 28 days after the NasoVAX/placebo dose, a sample will be collected for viral culture as clinically indicated.

One interim analysis of humoral immunogenicity data and safety data (including summaries of AE, reactogenicity, concomitant medications and vaccines, vital signs, ECG, and laboratory data and listing of any viral culture results) will be conducted when all data through the Day 29 visit is available and monitored for all subjects.

A complete schedule of procedures and assessments for study ALT-103-201 is in Table 4-2.

ALT-FLZ-401, Extent and Durability of Immune Response Following Seasonal Influenza Vaccination in Healthy Volunteers, was an open label study designed to generate an immunogenicity sample set similar to that of ALT-103-201 in subjects receiving a licensed influenza vaccine based on the same H1 strain (A/California 2009). The seasonal vaccine H1 component changed at the time of the ALT-103-201 study to A/Michigan, so it was logistically much easier to conduct this study non-contemporaneously with the seasonal vaccine licensed for use in 2016-17. The same site, entry criteria and schedule of assessments for immunogenicity were followed. Twenty subjects were enrolled and samples from this study were frozen and stored and then shipped to blinded laboratory for immunogenicity testing in parallel to the samples from ALT-103-201. The schedule of events for ALT-FLZ-401 is in Table 4-3.

Table 4-2. ALT-103-201 TIME AND EVENTS SCHEDULE

Study Visit	Screening	Dosing Period							Follow-up Period	
		Day 1		Day 2 ^a	Day 4	Day 8	Day 15	Day 29	Day 91	Day 181
Window (days)	Day -28 to Day -1	Predose	Postdose		± 1	± 1	± 1	± 3	± 10	± 10
Informed consent	X									
Demographics	X									

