8.5.2 Adverse Events

The number and percent of ALT-103-201 subjects with any TEAEs will be displayed by SOC and PT for each dose group. Within each PT, subjects will be counted only once if they had more than one event reported during the treatment period.

The number and percentage of subjects with any TEAE will be presented as well as the corresponding 95% Clopper-Pearson exact CI of the percentage.

For MedDRA SOC, the number and percentage of subjects experiencing at least one TEAE overall and at least one TEAE for a system will be tabulated by severity grade (Grades 1-4) and dose group. For MedDRA PT, the number and percentage of subjects reporting at least one TEAE within a PT category will be tabulated by relationship to study products and dose group. For the calculations in these tables, each subject's TEAEs will be counted once under the maximum severity or the strongest recorded causal relationship to study product.

Summaries will be generated for all serious TEAEs, TEAEs resulting in dose withdrawal, treatment emergent MAEs, and treatment emergent NCI, by SOC and PT for each dose group.

A listing will be produced for all subjects who reported serious TEAEs. The listing will provide details of the events including severity, relationship to study product, time between onset and last study treatment administration, and a summary of the event.

All TEAEs and non-treatment emergent AEs will be listed individually by subject.

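### SAP 7.4.5 and 8.5.2 count any TEAE with no end date, so as written no listed table gives the Day 1 to Day 29 adverse event component of the ALT-103-201 primary endpoint

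*SAP*

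**What the plan says.** All of this concerns ALT-103-201; SAP 8.5 confines the safety analyses to that study.

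- **Endpoint (SAP Section 3).** The AE component of the primary endpoint is "Adverse Events (AEs): counts and percentages of subjects with AEs from Day 1 to Day 29". MAEs, SAEs and NCIs form a separate component with a longer window, ending in "new-onset chronic illness (NCI) from Day 1 to Day 181".
- **Collection (SAP Section 4).** "All AEs and medications will be recorded from signing of the informed consent form to Day 29". After that the scope narrows: "Thereafter to the end of the study, only MAEs, NCIs, SAEs, immunosuppressive medications (see list in Appendix 3), and vaccines will be recorded". Table 4-2 agrees, with one row for full AE assessment up to Day 29 and another for MAE/NCI/SAE assessment at Days 91 and 181.
- **Definition (SAP 7.4.5).** "Treatment Emergent Adverse Events (TEAEs) include all AEs that start on or after vaccination". AEs present before vaccination whose severity or relationship increases afterwards also count. No end date is given for either.
- **Tables (SAP 8.5.2).** "The number and percent of ALT-103-201 subjects with any TEAEs will be displayed by SOC and PT for each dose group". The section also asks for the overall any-TEAE percentage with a Clopper-Pearson interval, and for tables by severity and by relationship. None has a window. In the SAP 10.1 list, no title among Tables 14.3.2.1 to 14.3.2.4 mentions Day 29.

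**The concern.** The endpoint and the tables meant to report it cover different periods, and the manner of collection changes between them. Through Day 29 every AE is recorded. After that, a non-serious event that is not a new chronic illness is recorded only if it was medically attended. Followed literally, the plan counts a subject whose only event is a medically attended illness in month four, but not a subject with the same illness who did not seek care.

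The resulting percentage is an unintended composite. It is neither the Day 1 to Day 29 AE rate nor a Day 1 to Day 181 rate under uniform collection. The primary objective is to describe safety, so a reader of the report would reasonably take the any-TEAE line as the stated primary component when it is not.

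**Working it through.** **1. The plan's own figures.** SAP 7.1 gives an 80% chance of seeing at least one AE that occurs at a rate of 3.6% among 45 NasoVAX subjects: 1 − (1 − 0.036)^45 = 0.808. It gives an upper bound of about 5% (one-sided 90%) if no SAE is seen: 1 − 0.10^(1/45) = 0.0499. Both reproduce. Neither depends on the TEAE window, so they do not bear on this point.

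**2. Windows side by side.**

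| Item | Source | Window |
|---|---|---|
| AE component of primary endpoint | SAP 3 | Day 1 to 29 |
| MAE, SAE, NCI component | SAP 3 | Day 1 to 181 |
| Full AE recording | SAP 4, Table 4-2 | consent to Day 29 |
| MAE, NCI, SAE recording only | SAP 4, Table 4-2 | after Day 29 to end of study |
| TEAE | SAP 7.4.5 | vaccination onward, no end |
| Any-TEAE, SOC/PT, severity and relationship summaries | SAP 8.5.2, 10.1 | none stated |

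On nominal visit days, selective collection covers 181 − 29 = 152 days, and 152/181 = 84% of the period.

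**3. Can TEAE be read as stopping at Day 29?** No. Section 8.5.2 also summarises treatment-emergent MAEs and NCIs, whose endpoint runs to Day 181. One definition serves both, so it cannot silently end at Day 29. The phrase treatment period in 8.5.2 is undefined and appears only in the rule that counts a subject once within a preferred term. Table 4-2 uses other period names.

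**4. Direction.** Both versions use the Safety Population as denominator, and every subject with a TEAE by Day 29 is counted in both. The open-ended any-TEAE percentage therefore equals or exceeds the Day 29 one, and it differs only if some subject's first event falls after Day 29. In the SOC/PT tables a cell also rises when the first event of that term is late. In the severity and relationship tables, a late event can move a subject to a higher grade or a stronger causal category, because the maximum is taken.

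**5. Size per subject.** Each dose group has 15 subjects, pooled placebo has 3 × 5 = 15, and all active doses together have 45 (SAP Table 4-1). One added subject is 1/15 = 6.7 points or 1/45 = 2.2 points.

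**6. Illustration only.** The documents give no AE rates, so both inputs here are assumptions. Let P29 be the Day 1 to 29 proportion, and q the chance that a subject free of AEs to Day 29 later has a recorded MAE, NCI or SAE. Then:

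P181 = P29 + (1 − P29) × q

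- P29 = 30%: P181 = 31.4%, 33.5%, 37.0% and 44.0% for q = 2%, 5%, 10% and 20%.
- Over P29 = 10% to 50% and q = 2% to 20%, the excess (1 − P29) × q runs from 0.50 × 0.02 = 1.0 point to 0.90 × 0.20 = 18.0 points.
- P29 = 30%, q = 5%: a subject is added with probability 0.70 × 0.05 = 0.035. The chance of at least one is 1 − 0.965^15 = 41% in a group of 15 and 1 − 0.965^45 = 80% in the pooled 45.

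**The case against.** The best reply is that the window is set and merely not repeated. Section 3 states it and Section 6.3 refers back to Section 3. Table 4-2 separates the two kinds of AE assessment. Section 7.4.7 limits early-termination safety data to Day 29 or before. The shells and programming notes are a separate document (SAP 10.2), and the ALT-103-201 protocol is not among the documents. Either might carry the cut-off.

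Part of this stands. The claim can only be about the plan as written; how the final tables were programmed cannot be known from these documents. But the cited text does not supply the window: Section 6.3 is only a pointer, and Section 7.4.7 concerns assignment of early-termination visits.

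Three stronger inferences are tempting, and the documents do not support them:

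- **That the open window dilutes a NasoVAX versus placebo comparison.** If late events were independent of early ones and equally likely in every arm, the arm difference would be multiplied by (1 − q). But 8.5.2 plans no between-arm AE difference or test, only per-group summaries. Equal late rates, and any particular AE rates, would be invented. The between-arm test in the safety section is the Kruskal-Wallis test on 14-day reactogenicity, which is unaffected.
- **That interim tables stop at Day 29 and so must disagree with the final ones.** Section 7.3 sets when the interim takes place but no event-level cut-off. Cohorts are sequential, so earlier cohorts could already have later events in the interim data.
- **That the whole primary safety endpoint is compromised.** Reactogenicity and the serious TEAE, MAE and NCI tables are unaffected, and every AE is listed by subject.

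**Conclusion.** The point holds for the plan as written. Sections 7.4.5 and 8.5.2 set no end to the TEAE window, Section 3 sets Day 29, and collection becomes selective after Day 29. The any-TEAE percentage with its interval, and the SOC/PT, severity and relationship tables, therefore mix two collection regimes, and no table in the SAP list delivers the stated Day 1 to Day 29 component.

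For the any-TEAE percentage the direction is certain: equal or upward, by 6.7 points per late-only subject in a group of 15 and 2.2 points in the pooled 45. The total is unknown, and the percentages under step 6 of the working only illustrate it under assumed rates. No planned test changes. The conclusion assumes that the unavailable shells and ALT-103-201 protocol do not impose the cut-off. Because this is a component of the primary endpoint and the correction is cheap, it should be made.

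**What to change.** In SAP 8.5.2, with a matching line in 7.4.5:

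1. Compute the any-TEAE percentage with its Clopper-Pearson interval, and Tables 14.3.2.2 to 14.3.2.4, for TEAEs that start, or worsen from a pre-vaccination state, from vaccination through the Day 29 visit. Naming worsening matters: a rule based on onset alone would drop pre-existing AEs that 7.4.5 counts.
2. Keep Day 1 to Day 181 for the serious TEAE, MAE and NCI tables (14.3.2.5, 14.3.2.7, 14.3.2.8).
3. Show severity and relationship for SAEs, MAEs and NCIs after Day 29, either in those tables or in a separate Day 30 to 181 row. They are planned by SOC and PT only, so cutting the severity and relationship tables at Day 29 would otherwise leave the later events untabulated on both.
4. Put the window in each table title and apply the same onset cut-off at the interim. Check that the shells agree.

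The cost is one onset-window flag in the AE analysis dataset, a few extra rows and a few words in the SAP. No new data are needed.

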
 To evaluate the mucosal immune response NasoVAX when administered by intranasal spray at a single dose of 1×10^9, 1×10^{10}, or 1×10^{11} vp 	
 Immunoglobulin A (IgA) antibody level measured by enzyme-linked immunosorbent assay (ELISA): 
 GMT GMR

 To evaluate the humoral immune response against nonrepresented influenza strains after NasoVAX administration 	
 Antibody level measured by HAI and MN in serum against each strain tested: 
 GMT GMR Responder rate: the number and percentage of subjects with 2-fold and 4-fold rise since baseline

 To evaluate the effect of predose adenovirus serotype 5 (Ad5) serum antibody levels on the immunogenicity of NasoVAX 	
 Predose Ad5 antibody GMT measured by MN in serum Day 29 GMR and responder rate from antibody level measured by HAI in serum

 To compare immunogenicity results to those obtained from banked samples from a previous study of licensed seasonal vaccine in a similar subject population (ALT-FLZ-401) 	
 Antibody level measured by HAI in serum: 
 GMT GMR SPR SCR Antibody level measured by MN in serum: 
 GMT Responder rate SFUs to hemagglutinin peptides measured by ELISpot in PBMCs: 
 Geometric mean SFUs Responder rate IgA antibody level measured by ELISA: 
 GMT GMR

4 Study Design

Study ALT-103-201 is a Phase 2a, randomized, double-blind, placebo-controlled trial to evaluate the safety, and immunogenicity of NasoVAX in healthy adults 18 to 49 years of age. Subjects will be screened within 28 days of randomization (Day 1). Approximately 60 subjects who meet all inclusion and no exclusion criteria and provide written informed consent will be enrolled into 3 sequential cohorts of 20 subjects each defined by the viral particle dose (1×10^9 , 1×10^{10} , and 1×10^{11} vp). Within each cohort and its sentinel group, subjects will be randomized in a 3:1 ratio to receive 1 intranasal dose of NasoVAX or placebo (Day 1) as shown in Table 4-1.

Table 4-1 NasoVax Study Design

Cohort	Dose (vp)	Number of Subjects	
		NasoVAX	Placebo
1	1×10^9	15	5
2	1×10^{10}	15	5

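### SAP 7.4.5 gives no class to a pre-existing AE that worsens on Day 1 after the dose: it meets neither the TEAE nor the non-TEAE definition

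*SAP*

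**What the plan says.** SAP Section 7.4.5 defines two classes of adverse event.

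- **Treatment-emergent, new onset:** "Treatment Emergent Adverse Events (TEAEs) include all AEs that start on or after vaccination".
- **Treatment-emergent, worsening:** "AEs that are present prior to vaccination, but their severity or relationship increases after the vaccination date".
- **Non-treatment-emergent:** events that had ended by the day before dosing, and events that "started prior to the vaccination but did not increase in severity or relationship during treatment".

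The same list defines concomitant medication with wording that includes the dosing day: "Concomitant medications include all medications that are taken on or after the date of vaccination".

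Other sections set the context:

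- SAP Section 4 gives one intranasal dose, on Day 1. It also states: "All AEs and medications will be recorded from signing of the informed consent form to Day 29". Table 4-2 schedules AE assessment both before and after the dose on Day 1, and the text of Section 4 has "vital signs measured 2 hours postdose and on Days 4, 8, 15, and 29".
- SAP Section 8.5 limits the safety analyses to ALT-103-201.
- SAP Section 8.5.2 builds its AE summaries on TEAEs. For serious events it adds: "A listing will be produced for all subjects who reported serious TEAEs".

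**The concern.** The two limbs of the TEAE definition use different clocks. The new-onset limb runs from the vaccination itself, while the worsening limb runs from the end of the vaccination date. The non-TEAE definition uses a third expression, a period of treatment, which the SAP does not define for a single dose. The classes therefore do not complement each other.

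At stake is whether a same-day worsening reaches the summary tables. By title, outputs 14.3.2.2 to 14.3.2.9 (eight of the nine in that series) are limited to treatment-emergent events, including the serious-event table and the serious-event listing. A programmer who follows the text literally would leave such an event out of all of them. A programmer who reasons from the non-TEAE bullet would put it in. The SAP should not leave that choice open.

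**Working it through.** The point concerns a classification rule, so the main check is to apply the definitions to each case.

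| Event | New-onset limb | Worsening limb (literal) | Non-TEAE definition | Class |
|---|---|---|---|---|
| Starts on Day 1 after the dose | met | not applicable | not met | TEAE |
| Present before dose, never worsens | not met | not met | met | non-TEAE |
| Present before dose, worsens on Day 2 or later | not met | met | not met | TEAE |
| Present before dose, worsens on Day 1 after the dose, no further increase | not met (started earlier) | not met (same date) | not met (it did increase) | **none** |

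The last row takes the hours after the dose as part of treatment, which is the ordinary meaning. If treatment were taken to begin on Day 2, the event would become a non-TEAE. Either way it is not a TEAE.

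**Can the last row occur?** Events are recorded from consent, screening can run up to 28 days before Day 1, and subjects are assessed before and after the dose on Day 1. The plan therefore collects the data that would show it. The documents do not say how often it would happen.

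**Does another section repair it?** None does. Two sections treat Day 1 as on-treatment: the AE endpoint in Section 3 runs from Day 1 to Day 29, and Section 7.4.8 imputes an unknown start day in the dosing month to the dose date. Neither addresses worsening.

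**Scale.** SAP Table 4-1 gives 15 subjects per NasoVAX dose, 45 active in total, and 3 × 5 = 15 on placebo, pooled under Section 7.4.2. The number affected is an assumption, taken here as 0 to 2 subjects in all.

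- Per subject in one dose group: 1/15 = 6.7 percentage points. Two in the same group: 2/15 = 13.3 points.
- Per subject among all active subjects: 1/45 = 2.2 points.
- Exact 95% interval, the form Section 8.5.2 uses for any TEAE: 0/15 gives 0 to 21.8%, and 1/15 gives 0.2% to 32.0%.

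These are maxima. Section 8.5.2 counts a subject once per row, so a subject with another TEAE in that row leaves the rate unchanged.

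**Serious events, against the SAP's own figures in Section 7.1.** The chance of at least one event in 45 at a rate of 3.6% is 1 − 0.964^45 = 0.808, against the stated 80%. The one-sided 90% upper bound with no events is 1 − 0.1^(1/45) = 4.99%, against the stated 5%. Both reproduce, and neither depends on the TEAE rule. If one serious event were omitted and the count read as zero, the bound would show 5.0% when one event in 45 gives 8.4% (exact binomial).

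**The case against.** The strongest reply is that this is a drafting mismatch with little behind it. Much of that reply stands.

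- **Intent.** A reader might infer that the SAP deliberately classes same-day worsening as non-treatment-emergent. The text does not support that. The non-TEAE bullet excludes any event that increased during treatment, which suggests that post-dose worsening was meant to count.
- **Immediate reactions.** A reader might infer that the rule removes immediate reactions to the intranasal dose, and so understates the primary safety endpoint. That is too broad. Symptoms such as nasal irritation, sneezing, congestion, cough and headache are solicited in a diary handed out after the dose on Day 1. Section 8.5.1 tabulates them with no TEAE condition, and Section 7.4.6 keeps them out of the AE counts unless serious. The reactogenicity part of the primary endpoint is untouched.
- **Direction.** A reader might infer a bias in favour of NasoVAX. The rule can only lower a group's TEAE count, but it applies to the 15 placebo subjects as well. An omission there would make NasoVAX look worse by comparison.
- **Affected outputs.** Not all eight outputs are realistic places for a loss. A new-onset chronic illness is unlikely to be a worsened pre-existing event.
- **Record and oversight.** Section 7.4 says that all collected data will be listed, and Listing 16.2.7 covers adverse events. The escalation review and stopping criteria in Section 4 use AE, grade and related-SAE data, not the TEAE flag.
- **Documents not supplied.** The ALT-103-201 protocol, its eCRF and the programming notes are not available here. If worsening is entered as a new record with a Day 1 onset, the new-onset limb captures it.

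What the reply does not remove is the gap in the written rule. No section supplied closes it, and the disagreement between the two bullets is itself a reason to align them.

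**Conclusion.** The point holds as a minor correction to wording. As written, an AE present before the dose that worsens later on Day 1 belongs to neither class. Read literally, it is left out of the ALT-103-201 TEAE summaries and the serious-TEAE listing. ALT-FLZ-401 has no TEAE tables and is not affected.

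The likely size is small: few or no subjects, and at most 6.7 percentage points per affected subject in a 15-subject group. The documents support no claim about the direction of a between-group bias, and no claim that events disappear from the record or from safety oversight.

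The conclusion rests on two assumptions: that worsening is kept on the original AE record, and that the programming follows the literal text. If either fails, the practical loss disappears, though the wording still needs to be aligned.

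**What to change.** Two edits to SAP Section 7.4.5:

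1. Change the worsening limb so that it covers events whose severity or relationship *increases on or after vaccination*. On Day 1, use the time of the change where it is collected. Where it is not, count a Day 1 worsening as treatment-emergent.
2. Define non-treatment-emergent AEs as all AEs that are not TEAEs, so that every event falls in exactly one class.

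The cost is a line or two of SAP text and a small change to the derivation of the TEAE flag, best made before programming. The documents do not show that times of severity change are recorded, so the default for missing times may do most of the work. The downside is that a few changes that in fact came before the dose on Day 1, with no recorded time, may be counted as TEAEs.
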